#### 4.7.2.3 Specific data group collection

##### *1. Baseline sociodemographic and clinical data*

- Date of birth
- Gender
- Address and postcode of residence of individual (including multiple if child lives between separate households)
- Socioeconomic Indexes For Areas (SEIFA) Index Relative Socioeconomic Disadvantage (IRSD) quintile for address/postcode (17)
- Parental level of education
- Psychosocial Assessment Tool
- Ethnicity
- Date of diagnosis
- HbA1c at diagnosis of T1D
- Presentation in Diabetic Ketoacidosis (DKA): Yes/No
- T1D antibody status
- Medical comorbidities and medications

##### *2. Glycaemic measures*

- HbA1c
- CGM metrics
  - % time in range (TIR) 3.9-10.0 mmol/L

- % time in tight range (TITR) 3.9-7.8 mmol/L
- % time above range (TAR) >10 mmol/L
- % time below range (TBR) <3.9 mmol/L
- Glucose Management Indicator (GMI)
- Mean Sensor Glucose
- Glycaemic Variability: Standard Deviation and Coefficient of Variation

### 3. *Device information/Insulin Delivery*

- Type of CGM/Pump device
- Source of pump (self-funded, philanthropic, private-health insurance, other)
- Total daily dose of insulin; % of basal and bolus insulin
- % CGM sensor wear time: 2-weeks and 3-months wear
- % time spent in closed loop system
- CGM/pump use cessation date and reason

### 4. *Anthropometric data*

- Height, weight, Body Mass Index

### 5. *Significant clinical events*

- Number of severe hypoglycaemic episodes
- Number of DKA episodes

### 6. *Health service utilisation and sick day information*

Data is available from the WA Health Patient Administration System, webPAS, and will be accessed through the Business Intelligence Unit. In addition a health utilisation questionnaire will be provided through REDCap.

- Emergency department attendances
- Hospital admissions (related and unrelated to T1D)
- Number of out-of-clinic telephone, telemedicine and face-to-face visits with PCH Diabetes clinical team
- Other health professional attendances (GP, mental health professional attendance, other specialist teams, etc)
- Sick days resulting in missed education/occupation (parent and child)

## 7. Questionnaires

### Psychological measures

Participants will be emailed a link for the following surveys to be completed online using REDCap.

- Anxiety: GAD-7 (parent, child >12 years) (18)
- Pittsburgh Sleep Quality Index (parent, child >12 years) (19)
- Diabetes Treatment Acceptance and Satisfaction Questionnaire (DTSQ) (DTSQ-Teen, DTSQ-Parent) (21)\*
- DTSQ Change (DTSQc) (DTSQc-Teen, DTSQc-Parent) (21)
- Hypoglycaemic Fear Survey (Child version) (22)

Type 1 Diabetes and Life Measure (T1DAL) (parent, child >8 years) (23) and Problem Areas in Diabetes (PAID) (Parent and Child Versions) (24) questionnaires are collected as part of routine clinical care at the PCH Diabetes Clinic.

### Health-economic measures

- Child Health Utility Instrument (CHU-9D) (parent of child <5 years, child >5 years) (20)

#### 4.7.3 Timeline of data collection:

Timeline outlining when each of the data/questionnaires will be collected is listed in the below table. Of note the data collection may not fall precisely at 3 month time-frames post pump start, but given routine follow-up occurs 3 monthly, would be expected to be at 3 monthly intervals +/- 6 weeks based on when the routine clinical appointment occurs.

Blue shade indicates data that is routinely collected through the PCH diabetes service and green shade indicates additional for this study.

	Baseline/ Consent	Pump start	3m	6m	9m	12m	15m	18m	21m	24m
Consent	X									
Sociodemographic and clinical data	X									
Sociodemographic and clinical data: Parental level of education	X									
Glycaemic measures		X	X	X	X	X	X	X	X	X
Device information/Insulin Delivery		X	X	X	X	X	X	X	X	X
Anthropometric data	X	X	X	X	X	X	X	X	X	X

	Baseline/ Consent	Pump start	3m	6m	9m	12m	15m	18m	21m	24m
Significant clinical events		X	X	X	X	X	X	X	X	X
Health Service utilisation & sick day information		X	X	X	X	X	X	X	X	X
Questionnaires										
T1DAL						X				X
PAID						X				X
GAD7		X				X				X
Pittsburgh Sleep Quality Index		X				X				X
DTSQ (and if participant withdraws with permission)		X				X				X
DTSQ (Change)						X				
Hypoglycaemia Fear Survey						X				X
CHU-9D		X				X				X

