## 1.1 Project Summary

Type 1 diabetes (T1D) is one of the most common chronic diseases of childhood. Improving lives of children and families living with T1D is a critical goal with expected benefits for the individual, caregivers, healthcare system and wider society.

Automated insulin delivery via an advanced hybrid closed loop (AHCL) system is accepted as the most effective management strategy, proven in clinical trials and real-world studies, wherein a continuous glucose monitor (CGM) provides glucose information to an insulin pump which can then adjust insulin delivery via an algorithm (housed in an application or in the pump). Due to the established glycaemic benefits, access to AHCL therapy is recommended for all children with T1D according to the latest international guidelines(1).

However, despite national subsidy for CGM, AHCL access in Australia is limited as insulin pumps are primarily self-funded or accessed via health insurance funds or philanthropic programs. This has led to significant inequity in accessing AHCL.

The Department of Endocrinology and Diabetes at Perth Children’s Hospital is implementing a new clinical model of care that will provide early access to AHCL to all children with a new diagnosis of T1D. This study aims to evaluate the impact of the new model of care through a combination of routinely collected clinical information and prospectively collected survey data. Glycaemic control at 6, 12 and 24 months post diagnosis in children with newly diagnosed T1D at Perth Children’s Hospital will be compared to a historical cohort (diagnosed prior to this new model of care). The psychosocial wellbeing of participants will be explored and described through prospectively collected data and cost-effectiveness of this model of care will be evaluated. The overall objective is to comprehensively evaluate a model of care providing early access to AHCL following diagnosis of T1D.

There are no potential ethical concerns in the proposed study.

[figure not shown]

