### 3 Project Aims / Objectives / Hypotheses

#### Specific Aims

1. To determine whether a model of care implementing equitable, early access to AHCL in the first 12 weeks post diagnosis of T1D, is associated with improved glycaemic outcomes, compared to recent historical controls, over the first 24 months post diagnosis.
2. To longitudinally assess disease burden, treatment satisfaction and psychosocial well-being in children and caregivers who are initiated on AHCL early post diagnosis of T1D, over the first 24 months post diagnosis.
3. To evaluate the cost-effectiveness of early, equitable AHCL access as a model of care in comparison to a previous model of care.
4. To investigate the feasibility of commencing AHCL within 12 weeks post diagnosis of T1D, specifically uptake and acceptance of early AHCL therapy and if applicable, the rates and reasons for discontinuation of AHCL.

We hypothesise that the new model of care will result in improved HbA1c at 6, 12 and 24 months post diagnosis of T1D as compared to the historical cohort. Furthermore, we hypothesise potential reduction in psychological distress and disease burden within the new model in comparison to recent historical control. We also hypothesise that the AHCL attrition rates will be low and the model will be cost-effective.

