### 4.2 Model of Care

The PCH Clinical Diabetes Service cares for all children in Western Australia with T1D as all individuals newly diagnosed with T1D are transferred to PCH given it is the only tertiary diabetes paediatric centre in the state.

The routine clinical pathway for individuals following T1D diagnosis at PCH includes:

- Brief admission at diagnosis for insulin injection initiation and basic education
- Multidisciplinary team led intensive outpatient education sessions through the Newly Diagnosed Diabetes Clinic
- Transition from this clinic at approximately 12-16 weeks post diagnosis to age group cohorts for those attending at clinics at PCH or outer metropolitan/regional cohorts for those living within these catchments, for ongoing 3 monthly outpatient follow-up as per gold standard recommendation

Individuals with T1D are offered, encouraged and assisted in considering AHCL systems at all points in the above clinical pathway by their diabetes team, unless a clinical decision made by skilled health care practitioners deems that AHCL is not an appropriate management strategy for an individual (for example; families with significant language barriers may not be able to successfully engage with pump system education which is primarily delivered in English and therefore use of AHCL may be deemed unsafe). The primary pathways for AHCL access as previously outlined are high tier private health insurance (approximately 25% of the total clinic cohort), self-funding, or exploration of eligibility for the philanthropic pathways. For individuals meeting these criteria, the clinical team aids them in navigating pump choice and commencement.

Within this model of care, choice is respected for all individuals in regard to insulin management strategy. Individuals self-funding insulin pumps are offered complete choice in their pump, with AHCL initiated where appropriate. For those accessing pumps via philanthropic pathways, pump choice is dependent on eligibility within the program. Finally, some individuals prefer MDI therapy and will not choose to wear a pump; once again, individual choice is always respected.

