### **4.7.2 Data collection**

#### 4.7.2.1 Routine clinical data collection

The WA Children's Diabetes Database (WACDD) stores clinical data from consenting individuals with T1D receiving care at PCH (see section 8.6 below for further details). This data includes clinical (anthropometric/glycaemic/insulin delivery) and sociodemographic data.

Consent for data sharing and research participation is sought from families at time of initial diagnosis of T1D (HREC Ref 2013051EP). Majority of the data proposed to be collected through this study are routinely collected at diagnosis and 3 monthly clinic visits and stored in WACDD.

Data which is routinely collected at these clinic visits will be exported (clinical data from WACDD, device information/insulin delivery/CGM data from proprietary software) at each of the timepoints below.

Of note while majority of the questionnaires planned for collection in this study are additional for study participants (see additional data collected below), Type 1 Diabetes and Life Measure (T1DAL) (parent, child >8 years) and Problem Areas in Diabetes (PAID) (parent and child versions) are already routinely collected clinical measures, also stored in WACDD.

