## 6.2 Efficacy assessment

A lower regression adjusted mean difference in HbA1c in the contemporary cohort as compared to historical control at 6, 12 and 24 months will be the primary efficacy assessment.

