A cost-effectiveness analysis of the new model of care compared to the previous model of care from a health care system perspective will be led by a co-investigator from Monash university with expertise in health economics. The main outcome of interest will be the incremental cost-effectiveness ratio which captures the mean differences in health outcomes and costs. Health outcomes will be measured by quality-adjusted life years (QALYs), calculated from the CHU-9D instrument. Data will be captured during the trial for the intervention (new model of care) group. The comparator (historical cohort) will not have CHU-9D data available as it was not historically captured. Therefore, we will use CHU-9D data collected on children with diabetes from the Longitudinal Study of Australian Children (LSAC) for quality of life in the comparator group. This is suitable given that LSAC data was collected under the previous model of care which exists in most states/territories (with limited access to AHCL). Other outcomes such as the number of significant events (including hospitalisations) averted will also be explored. Costs include the cost to deliver the new model of care, and the cost of health care services used by participants during the time horizon of the trial (including hospitalisations and emergency department attendances) costed using standard Australian unit prices. Standardised economic evaluation techniques including bootstrapping to determine confidence intervals will be employed. The results of our analysis will also be used to do a budget impact analysis to estimate the financial consequences of adopting the new model of care.

Final analysis will occur after the final study participant has completed the 24 month data collection, however interim analyses will occur approximately 6 monthly from initial pump start in the contemporary cohort.

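### The HbA1c comparison is timed from diagnosis but the collection schedule is timed from pump start, and the schedule gives children who never start a pump no baseline for the questionnaires first due at pump start

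*Protocol*

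**What the plan says.** Two time origins appear in the protocol.

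- **Diagnosis.** Section 1.1 announces a comparison of "Glycaemic control at 6, 12 and 24 months post diagnosis in children with newly diagnosed T1D". The hypothesis in section 3 expects "improved HbA1c at 6, 12 and 24 months post diagnosis of T1D as compared to the historical cohort". Aims 1 and 2 in section 3 also cover the first 24 months from diagnosis.
- **Pump start.** Section 4.7.3 says that "the data collection may not fall precisely at 3 month time-frames post pump start" and that visits "would be expected to be at 3 monthly intervals +/- 6 weeks based on when the routine clinical appointment occurs". In its table, the glycaemic, device, clinical-event and health-service rows have their first mark in the pump-start column, followed by 3m to 24m. Section 4.7.2.1 says that routine data, including the clinical data in the state diabetes database (WACDD), will be exported "at each of the timepoints below". The 4.7.3 table is the only schedule that follows.

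The sections that define the analysis do not settle the matter. Section 6.2 says that the adjusted difference "as compared to historical control at 6, 12 and 24 months will be the primary efficacy assessment" but gives the months no origin. Section 8.1 makes 24-month HbA1c the regression comparison and calls 6 and 12 months interim, again without an origin.

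On children without a pump, section 4.2 expects that "some individuals prefer MDI therapy and will not choose to wear a pump". Section 8.5 nevertheless includes all newly diagnosed participants in the primary analysis.

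**The concern.** A comparison of two cohorts at a fixed time needs the same time zero in both. Pump start cannot serve for the historical cohort. Section 2 puts those starting the device in the newly diagnosed period at about one third of a yearly cohort, with a mean start of 9.37 months in 2022. Its 6-, 12- and 24-month values can in practice be dated only from diagnosis. If the contemporary values followed the schedule instead, the cohorts would be compared at different points in the disease course, with a shift in one direction that the visit window does not average out.

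The second issue is the items first collected at pump start: GAD-7, the sleep index, DTSQ and CHU-9D. A child who stays on injections has no pump start, so the schedule never says when the first of these is due. CHU-9D matters most, because section 8.1 calculates the QALYs for the new model of care from it. If only pump users have CHU-9D, the economic result describes the device rather than a model of care that some families decline.

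**Working it through.** The protocol states no figure for the offset, so there is none to reproduce. Its only benchmark is the 0.35-point effect in section 8.2. The power claimed for that effect cannot be reproduced, because no SD is given.

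**Inputs from the protocol**
- Target delay from diagnosis to pump start: up to 12 weeks (4.7.1).
- Mean delay in 2023: 3.55 months (section 2).
- Visit window: ±6 weeks (4.7.3).
- Last eligible diagnosis: 31 March 2025 (4.3). Study start: 22 April 2024 (section 1). Duration: 36 months (4.8).
- Consented contemporary cohort: 105-121 (8.2).

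**Assumptions, not in the protocol**
- HbA1c slope of 0.03-0.10 points per month in the first year.
- 10-20% of consented children never start a pump.

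**Step 1: offset, if contemporary values follow the schedule and historical values follow diagnosis**
- 12 × 7 / 30.4375 = 2.76 months. The window is 6 × 7 / 30.4375 = 1.38 months.
- Week-12 starter: 6 + 2.76 = 8.8, 12 + 2.76 = 14.8 and 24 + 2.76 = 26.8 months after diagnosis.
- At the 2023 mean delay: 9.55, 15.55 and 27.55 months.
- With diagnosis as origin in both cohorts, the systematic offset is 0 and only the ±1.38-month window remains.

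**Step 2: illustrative HbA1c shift**
- Shift = slope × offset: 0.03 × 2.76 = 0.08 points; 0.10 × 2.76 = 0.28 points.
- Against the 0.35-point effect: 0.083 / 0.35 = 24%; 0.276 / 0.35 = 79%.
- The slope that counts is the contemporary cohort's own over those weeks. Section 2 says only that HbA1c has risen above target in most children by 12 months. That supports a direction (against the new model at 6 and 12 months) but gives no rate.

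**Step 3: are diagnosis-dated HbA1c values available?**
- For a week-12 starter, the 3m, 9m and 21m columns fall at 3 + 2.76 = 5.76, 9 + 2.76 = 11.76 and 21 + 2.76 = 23.76 months after diagnosis, well inside the window around 6, 12 and 24.
- Glycaemic measures are marked in all three columns, so the values exist and only the rule for choosing them is unclear.

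**Step 4: CHU-9D**
- It is marked only at pump start, 12m and 24m, so no neighbouring column can stand in.
- If 10-20% never start: 0.10 × 105 = 10.5 to 0.20 × 121 = 24.2, or about 11 to 24 consented children with no defined first questionnaire.

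**Step 5: calendar**
- Thirty-six months from 22 April 2024 ends in April 2027.
- The last child reaches 24 months after diagnosis on 31 March 2027, inside that period.
- With a week-12 start on 23 June 2025, 24 months after pump start is 23 June 2027, outside it.
- The stated duration therefore fits the diagnosis clock and not the pump-start clock. The finish date of 21 April 2026 in section 1 fits neither and is a separate matter.

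**The case against.** The strongest reply is that the schedule governs when data are collected and exported, not which value is analysed. Wherever the cohort comparison names an origin, it is diagnosis. Both cohorts come from WACDD, which is filled at diagnosis and at 3-monthly visits whatever the pump status (4.7.2.1, 8.1). Date of diagnosis is recorded (4.7.2.3), HbA1c is measured every 3 months (6.1), and step 3 shows that suitable values will exist. Section 8.1 says that "interim analyses will occur approximately 6 monthly from initial pump start in the contemporary cohort", but that fixes when analyses are run rather than how a child's value is chosen. Mapping visits to analysis windows is commonly left to an SAP.

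Most of this stands, and it rules out two stronger readings that a reader might infer. The first is that contemporary HbA1c will in fact be read later than historical HbA1c. No section says that the analysed value is picked by pump-start month. The second is that children who never start a pump drop out of the HbA1c comparison and so flatter the new model. Section 8.5 keeps them in, and their routine 3-monthly HbA1c remains available.

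Two things survive the reply. The protocol contradicts itself on the origin, and section 6.2, where the primary assessment is defined, does not resolve it. A later SAP can also re-date HbA1c but cannot recover questionnaires that were never sent. The psychosocial measures are analysed descriptively within the contemporary cohort, and Aim 2 concerns children who start the device, so the non-starter gap falls mainly on the cost-effectiveness aim.

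**Conclusion.** The concern holds in this limited form. The diagnosis origin in sections 1.1 and 3 conflicts with the pump-start origin in 4.7.3, to which the exports are tied. Any offset is conditional on contemporary values being taken by the schedule and historical values by diagnosis date. It would then be about 2.8 months for a week-12 start, less for earlier starters and more for later ones. The 0.08-0.28 points is an illustration that rests on an assumed slope and on the longest delay within the 12-week target; it is not an estimate of bias. The shift is probably smallest at 24 months, the main regression comparison, if the HbA1c curve has flattened by then. The gap in the first CHU-9D, GAD-7, sleep index and DTSQ for non-starters follows directly from the schedule. Only the number of children affected is assumed.

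**What to change.** - In 4.7.3, 6.2 and 8.1, state that date of diagnosis is time zero for HbA1c, clinical events and costs in both cohorts. Use the value closest to 6, 12 and 24 months within the existing ±6 weeks.
- Keep the pump-start clock for device metrics only, and say so in the table.
- Set a fixed baseline questionnaire time, counted from diagnosis, for participants who do not start a pump (12 weeks after diagnosis is one option). CHU-9D, GAD-7, the sleep index and DTSQ then have a defined first collection for them, and later rounds can follow from it.

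The cost is protocol wording, an extraction rule and a change to the questionnaire timing for non-starters. HbA1c is already measured every 3 months, so no visits are added. The downside is that some questionnaires shift by a few weeks relative to HbA1c.

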#### 4.8 Project Duration/Schedule

This study will be completed within 36 months. Participants will be enrolled in the study for 24 months, as detailed in Section 4.6.

## 5 Treatment of Participants

### 5.1 Description and justification for treatments, interventions or methods to be utilised

There are no new treatments or interventions in this study.

This project is considered to be low burden on the participant and family as much of the data is already being collected clinically as highlighted in the table above. The additional measures including psychosocial questionnaires will be collected using REDCap, allowing participants to respond in an environment which is convenient for them.

### 5.2 Permitted medications/treatments

Participants will continue their usual medications and treatments for the duration of the study including insulin and emergency hypoglycaemia management as prescribed by their diabetes team.

## 6 Assessment of Efficacy

### 6.1 Outcomes

Glycaemic control will be measured by HbA1c measured every 3 months utilising the DCA Vantage HbA1c analyser.

## 6.2 Efficacy assessment

A lower regression adjusted mean difference in HbA1c in the contemporary cohort as compared to historical control at 6, 12 and 24 months will be the primary efficacy assessment.

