# 8 Data Management, Statistical Analysis and Record Keeping

## 8.1 Statistics and Interim Analysis

The cohort newly diagnosed with T1D in the 12 months following study start (the contemporary cohort) will be compared to a historical control (the cohort newly diagnosed between March 2022 and March 2023). Routine clinical data for both cohorts will be extracted from WACDD. Descriptive statistics (mean/SD, median/IQR, or frequency/% as appropriate) will be presented for key demographic and clinical measures. The 24-month HbA1c in the contemporary cohort will be compared to the historical control through multivariable regression model adjusting for potential imbalances in clinical/sociodemographic characteristics. The adjusted mean difference along with 95% confidence intervals will be calculated. A sensitivity analysis using an inverse probability of treatment weighted regression based on propensity score will also be conducted.

Interim analyses employing similar models examining HbA1c difference between the cohorts at 6 and 12 months will be conducted. Further exploratory analyses presenting mean HbA1c over various clinical factors (e.g. urban/remote postcode/SEIFA, insurance status, age at diagnosis, timing of HCL commencement, etc) will also be conducted. Subanalysis reviewing mean HbA1c on those commencing on AHCL within 12 weeks from diagnosis will similarly be examined.

Device uptake and attrition will be presented as frequencies and proportions along with 95% confidence intervals. Bivariate predictors of device use at uptake will be presented through simple contingency tables of device use by clinical and sociodemographic factors (Age group ( $\leq 12$  years,  $> 12$  years), gender, socioeconomic indices for areas quintile (lowest quintile, other 4 quintiles), DKA at diagnosis).

Simple descriptive statistics (mean/SD, median/IQR, or frequency/%) will be presented for CGM metrics and psychosocial measures at each of the follow-up points for the contemporary cohort. Where appropriate, mixed models or non-parametric Friedman tests will be conducted to assess within person change over time.

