## **8.3 Study Power and Significance**

P values of <0.05 will be used to determine statistical significance and 2-sided P-values will be reported. Corrections for multiple comparisons will not be employed.

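### Sections 6.2 and 8.1 disagree on whether HbA1c at 6 and 12 months is primary or interim, so the error rate and power of the primary claim are not fixed

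*Protocol*

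**What the plan says.** The protocol gives the same three comparisons two different statuses.

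- **Section 3 (hypotheses)** joins the timepoints: "We hypothesise that the new model of care will result in improved HbA1c at 6, 12 and 24 months post diagnosis of T1D".
- **Section 6.2** makes all three primary: the adjusted HbA1c difference "as compared to historical control at 6, 12 and 24 months will be the primary efficacy assessment". It gives no ordering and does not say whether one or all must succeed.
- **Section 8.1** starts from a single timepoint: "The 24-month HbA1c in the contemporary cohort will be compared to the historical control through multivariable regression model". It then gives the other two a lesser status: "Interim analyses employing similar models examining HbA1c difference between the cohorts at 6 and 12 months will be conducted".
- **Section 8.1, on timing:** "Final analysis will occur after the final study participant has completed the 24 month data collection", while "interim analyses will occur approximately 6 monthly from initial pump start in the contemporary cohort". No early-success or stopping rule is attached to these looks.
- **Section 8.2** claims power above 80% for a difference greater than 0.35% HbA1c in one primary analysis. It names neither the timepoint nor a standard deviation.
- **Section 8.3** fixes the testing rule: "P values of <0.05 will be used to determine statistical significance and 2-sided P-values will be reported", and "Corrections for multiple comparisons will not be employed".

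**The concern.** A primary claim has a known error rate only when the protocol says which result or combination of results constitutes success. Here three readings are open: success at any of the three timepoints, success at all three, or success at 24 months alone. Section 6.2 fits the first two and section 8.1 fits the third.

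The readings have different error rates and different power, and nothing in the protocol prevents the choice being made after the 6- and 12-month results are known. Those results arrive well before the 24-month data, which makes the ambiguity more than a matter of labels. Section 8.3 also closes the usual way out, since it rules out any correction if three timepoints are kept.

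**Working it through.** **Inputs from the protocol.** Two-sided alpha 0.05, uncorrected (8.3); three timepoints (6.2); 130-150 children per year and a historical cohort of similar size (8.2); target difference 0.35% and power above 80% (8.2).

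**Assumptions.** The protocol gives no HbA1c standard deviation and no between-visit correlation. The SD is back-solved or varied. The three test statistics are given a common correlation ρ between 0 and 0.9.

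**1. The stated power.** With n per cohort, power = Φ(0.35 / (SD·√(2/n)) − 1.960). The largest SD that gives 80% is 0.35 / ((1.960 + 0.842)·√(2/n)):

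- n = 130: 0.35 / (2.802 × 0.1240) = 1.007
- n = 150: 0.35 / (2.802 × 0.1155) = 1.082

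At SD 1.0, power is 80.6% (n = 130) and 85.8% (n = 150). At SD 1.2 it is 65.2% and 71.4%. The claim is attainable for one timepoint but cannot be reproduced without an SD.

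**2. Any timepoint suffices.** If the tests were independent, the error would be 1 − 0.95³ = 14.3% two-sided, and 1 − 0.975³ = 7.3% counting only results that favour the new model. For correlated tests, write Z = √ρ·U + √(1−ρ)·E for each timepoint, with U shared, and average over U: error = 1 − E[P(|Z| ≤ 1.960 given U)³].

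**3. All three required.** With no effect anywhere, error is the probability that all three tests are significant. Joint power is the probability that all three are significant in the favourable direction when each has mean 1.960 + 0.842, which is 80% power each. At ρ = 0 that is 0.8³ = 51.2%.

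| Assumed ρ | Any: two-sided error | Any: favourable direction | All: two-sided error | All: joint power |
|---|---|---|---|---|
| 0 | 14.3% | 7.3% | 0.01% | 51% |
| 0.5 | 12.5% | 6.3% | 0.3% | 61% |
| 0.7 | 10.9% | 5.5% | 0.9% | 66% |
| 0.8 | 9.8% | 4.9% | 1.4% | 69% |
| 0.9 | 8.4% | 4.2% | 2.3% | 72% |

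The reference values for a single test are 5% two-sided and 2.5% in the favourable direction. If there is an effect at some timepoints but not all, the all-required rule can err more often than the table shows. It never exceeds 5%, because the test at the timepoint with no effect must itself be significant.

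**4. 24 months alone.** This is one final test at 0.05, so error is 5.0%, and the power figures in step 1 stand as they are.

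**The case against.** The strongest reply is that this is a conflict of labels in a non-randomised evaluation of a care model that the service is already adopting. Interim results trigger no stopping or allocation decision, the absence of correction is declared openly, and section 8.1 commits to adjusted differences with 95% confidence intervals. Sections 3 and 6.2 join the timepoints with the word *and*, which does not suggest that any one is enough. An any-or-all rule may also sit in a statistical analysis plan that is not shown.

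Much of this stands, and it limits the point in three ways.

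- **A reader might infer that the error rate is simply not 5%.** The protocol does not support that. It holds only if any timepoint can carry the claim, which no section says. Nor does 8.1 call 24 months primary; that follows from its layout and from the timing of the final analysis.
- **A reader might infer that the 6-monthly looks inflate the 24-month test.** Interim tests of 6- and 12-month HbA1c concern different endpoints, and no rule lets an early look declare success. Diagnoses run from 1 April 2024 to 31 March 2025 (4.3), so each timepoint's data accrue over about 12 months and could be seen at only two or three looks before they are complete. A long series of tests on one accumulating endpoint does not fit that schedule.
- **A reader might count the team presentations in section 10.2 as further efficacy looks.** That section concerns quality control and does not describe comparisons between cohorts.

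The contradiction itself remains. Which timepoint is primary is a protocol-level definition, and a later analysis plan could not follow both 6.2 and 8.1. Section 8.3 has already settled the multiplicity question, so it has not been left for later.

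**Conclusion.** The concern holds in a limited form: the protocol does not fix its primary timepoint, and so does not fix the error rate or power of its primary claim. The two-sided error is about 8-14% if any timepoint suffices, no more than 5% if all three are required, and 5% if 24 months alone is primary. In the favourable direction, the any-timepoint figure is about 4-7% against 2.5%. Under the all-required reading, joint power of about 51-72% means that the >80% in section 8.2 would not describe the primary assessment.

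The ranges rest on assumed equal correlations of 0 to 0.9 between timepoints and, for joint power, on exactly 80% power at each. The contradiction between sections depends on neither assumption. It should be resolved before any comparison between the cohorts is seen.

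**What to change.** - Name one primary timepoint in the same words in sections 6.2, 8.1 and 8.2. Choosing 24 months matches the present layout of 8.1 and leaves the power statement as it is.
- Make 6 and 12 months secondary, reported as adjusted differences with 95% confidence intervals. If formal tests are wanted, place them in a fixed sequence after the primary.
- State in 8.1 that the 6-monthly interim analyses carry no primary efficacy claim.

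This is a change of wording with no change in sample size. Its cost is that one timepoint carries the claim. The hypothesis in section 3 can stay, provided that the text makes clear which part of it is the primary test.

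If the team prefers three primary timepoints, section 6.2 needs an explicit rule and section 8.2 a matching power statement. Splitting alpha equally (0.05/3 = 0.0167 each) would require section 8.3 to change. At an assumed SD of 1.0, power per timepoint would fall from 80.6% to 66.6% (n = 130) or from 85.8% to 73.8% (n = 150). Reaching 80% would take 171 per cohort instead of 129, more than the 130-150 that section 8.2 expects in a year.
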